## **11.5 Core Laboratory for Evaluation Tests**

A core lab shall be used for the objective evaluation of both symptomatic and asymptomatic arrhythmia recordings. The core lab will be instructed to prioritize analysis of asymptomatic recordings in the event that progression to persistent AF/AT has occurred without the subject's awareness. Initial evaluation of TTM recordings will be performed by technical personnel trained in the evaluation of these recordings and will be reviewed by a cardiologist or an experienced EP technician. If asymptomatic AF is present, the subject will be contacted immediately to start daily TTM recordings for 7 consecutive days. AF/AT episodes will be evaluated per the definitions provided in this protocol (refer to Study Definitions).

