#### **15.5 Clinical Endpoint Committee (CEC)**

The Sponsor may consider to assign a Clinical Endpoint Committee (CEC) to adjudicate the primary event outcome.

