#### **15.6 Data Safety Monitoring Committee (DSMC)**

An independent DSMC, consisting of 3 physicians, at least one of which must be expert in electrophysiology, will meet according to a defined schedule to review interim analyses of both safety and effectiveness parameters, and for purposes of advising the study sponsor as to whether the study should continue or be suspended/terminated. Telephone conferences may be initiated outside the defined schedule to discuss serious study issues that may have arisen.

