4. ANALYSES AND REPORTING

4.1 Interim Analyses

An interim examination of the primary endpoint data will be performed at regular time intervals during the course of the trial to determine whether the study will be stopped for effectiveness or futility. Interim analyses will only be presented for the ITT and Safety Population. At the first interim analysis, sample size adjustment will be considered as specified in section 5. In addition, statistical interim reporting will also involve a review of adverse events. The results of the interim analyses will be reviewed by the Global Safety Monitoring Committee (GSMC) of Biosense Webster.

The GSMC will review the accumulated data no earlier than 1 year following the

study start and then approximately every 6 months thereafter if enrollment was on target. Data for the primary effectiveness endpoint and adverse events will be reviewed. Extracted data files and analysis programs for each interim report will be archived in the study files. Further details on the planned interim analyses are given in section 10.4. Moreover, it is indicated in the table of contents (section 15) which subset of tables, listings and figures will also be produced for the interim analysis.

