8.3 Derived Variables

Duration of AF [months]

Time between the recorded date of first AF and the date of randomization.

Time to persistent AF/AT

According to protocol, persistent AF/AT is defined as AF/AT lasting longer than 7 consecutive days or requiring termination by cardioversion after 48 hours. The primary endpoint is reached at the date of the first cardioversion after randomization (except cardioversion solely as part of a (re-)ablation procedure) or detection of persistent AF/AT by transtelephonic monitoring (TTM, performed between month 3 and month 36). The sponsor will review and adjudicate all events (progressions to persistent AF/AT), which were reported by the Investigator. Adjudication will already be performed for the interim analyses. All events where the sponsor confirmed in their final assessment that the primary endpoint was reached will be taken into account for analysis. The date at which the primary endpoint was reached will be taken as adjudicated by the sponsor or as reported by the Investigator (if no sponsor adjudicated date is available).

The protocol is not specific about the start date for time to event calculation. Originally according to SAP version 1.0 (which was applied for the interim analyses) time to event had been defined as the difference between randomization date and the date at which the endpoint was reached. However, after further discussion, it was decided to update the start date for time to event calculation for final analysis and to use date of procedure as start date for the test group, and date of randomization as start date for the control group.

This approach seems to be more appropriate and more conservative, as visit windows are calculated from date of procedure for test group. Otherwise, if time to event was calculated from date of randomization, test group would have longer follow-up period and longer time to each follow-up visit as control group.

If the primary endpoint is not observed during follow-up time, subjects will be regarded as censored at the completion visit/ last visit or at the last time TTM was recorded, whichever is later.

Time to persistent AF (HRS 2017)

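### Primary-endpoint events are confirmed and dated by the sponsor in an open-label trial, with no stated masking, no described route for events not reported as progression, and no analysis of events before confirmation

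*SAP*

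**What the plan says.** **Adjudication.** SAP 8.3 (Time to persistent AF/AT) first defines the endpoint from data: the first cardioversion after randomization, other than one done solely as part of an ablation, or detection of persistent AF/AT by transtelephonic monitoring (TTM). It then says "The sponsor will review and adjudicate all events (progressions to persistent AF/AT), which were reported by the Investigator". On what counts: "All events where the sponsor confirmed in their final assessment that the primary endpoint was reached will be taken into account for analysis". On timing: "The date at which the primary endpoint was reached will be taken as adjudicated by the sponsor", with the investigator's date used where there is none. On the interim looks: "Adjudication will already be performed for the interim analyses".

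**Masking and independence.** SAP 3.4 says the study is open-label. Protocol 11.4.1 and 11.4.2 provide for a determination that progression has occurred, made for Control subjects by the investigator. Protocol 15.5 says the sponsor "may consider to assign a Clinical Endpoint Committee (CEC) to adjudicate the primary event outcome". In the SAP such a committee appears only in the title of listing 16.2.17.2, the CEC adjudication form.

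**Other sources of events.** Protocol 11.5: "A core lab shall be used for the objective evaluation of both symptomatic and asymptomatic arrhythmia recordings". TTM covers both arms (Protocol 11.2.1). Cardioversions are documented at every follow-up contact (Protocol Table 1) and listed in SAP listing 16.2.31.

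**Interim results.** SAP 4.1 says these "will be reviewed by the Global Safety Monitoring Committee (GSMC) of Biosense Webster". Protocol 15.6 instead provides for "An independent DSMC, consisting of 3 physicians". SAP section 5 does not mention the change. Protocol 13.9.2 has the sponsor run the interim analyses.

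**The concern.** The primary result depends on two human steps, report and confirmation, and neither is described as masked. Some judgement is unavoidable. The onset of an episode must be placed to apply the 48-hour condition, and the SAP sentence that dates the endpoint at the first cardioversion does not repeat that condition, so adjudication has to supply it. Routine TTM is weekly to Day 300 and monthly afterwards, becoming daily once AF is seen or symptoms occur.

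If reporting or rejection differs by arm, the event counts are biased directly. Rejection may also be hard to reverse. Once progression is determined, arrhythmia monitoring is no longer required and the subject need only return at 3 years (Protocol 11.2.1, 11.4.1, 11.4.2), and no text restarts monitoring if the event is then rejected. Under the SAP 8.3 censoring rule such a subject could count as event-free through a largely unmonitored period.

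No planned analysis would reveal the effect. The HRS 2017 sensitivity analysis (SAP 8.3 and 10.5) also rests on sponsor adjudication.

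**Working it through.** **Inputs.** Planned 3-year progression after cross-over dilution is 5% Test and 15% Control, with one-sided alpha 0.025, 85% power and 322 subjects (161 per arm) (SAP 6). The final look has 28 events and bound 2.0507 (SAP 10.4 table). Rejection shares are assumptions, because the documents give none.

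**1. The plan's own event count.** Hazard ratio = ln(0.95)/ln(0.85) = 0.3156, so δ = 1.153 (the plan prints 1.154). Schoenfeld: 4(1.960 + 1.036)²/1.153² ≈ 27.0, which at the unrounded δ is just above 27 and rounds up to the plan's 28. The Rubinstein-Gail-Santner formula, with 1.5 years' accrual and follow-up to study end, gives 291.0 subjects, and 291.0/0.90 = 323.4, close to 322.

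**2. How few decisions matter.** With similar exposure in the two arms, Z ≈ (C − T)/√(C + T), where C and T are Control and Test events. The table shows the smallest number of one-arm rejections that moves Z across 2.0507.

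| Reported C v T | Z | Rejected | Z after |
|---|---|---|---|
| 19 v 9 | 10/√28 = 1.89 | 1 Test (19 v 8) | 11/√27 = 2.12 |
| 18 v 10 | 8/√28 = 1.51 | 3 Test (18 v 7) | 11/√25 = 2.20 |
| 16 v 12 | 4/√28 = 0.76 | 6 Test (16 v 6) | 10/√22 = 2.13 |
| 20 v 8 | 12/√28 = 2.27 | 2 Control (18 v 8) | 10/√26 = 1.96 |
| 21 v 7 (planned 3:1 ratio) | 14/√28 = 2.65 | 4 Control (17 v 7) | 10/√24 = 2.04 |

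**3. Average effect over repeated trials.** Log-rank simulation: 161 per arm, 3 years' follow-up, exponential 10% dropout, 20,000 runs per case and one test at 2.0507. A rejected subject counts as event-free to the censoring time. With no rejection this setting yields about 30.6 events.

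| Assumed rejection | Positive result, no true difference (10% v 10%) | Power, planned effect (5% v 15%) |
|---|---|---|
| None | 1.8% | 82.6% |
| 10% in both arms | 2.0% | 77.9% |
| 20% in both arms | 2.0% | 72.4% |
| 10% of Control only | 0.9% | 70.6% |
| 10% of Test only | 3.8% | – |
| 20% of Test only | 7.3% | – |
| 30% of Test only | 13.4% | – |

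Equal rejection leaves the false-positive rate about where it was and costs power. Unequal rejection distorts the test, in whichever direction the inequality runs. The last column is blank for Test-only rejection because the higher rejection rate there is partly bias.

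**The case against.** The best defence is that much of the worry is inferred from silence.

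- **Events can only be removed.** A reader might infer that adjudication can never add an event, or that investigators select what to report. The documents do not say so. SAP 8.3 defines the endpoint from cardioversion and TTM data. The core laboratory reads both arms and gives priority to asymptomatic recordings, AF on TTM triggers 7 days of daily recording, and source verification is part of monitoring (Protocol 14.4). What stands is narrower: no text says how a finding not reported as progression reaches adjudication.
- **The process favours the device.** Confirmation that works equally in both arms does not, as the simulation shows. Inequality is needed, and none is documented.
- **The adjudicators know the interim results.** Nothing places adjudicators on the GSMC or says they see its output. The GSMC's independence is undescribed, not disproved, and adjudicating before an interim look is ordinary practice. What stands is an unreconciled conflict with the protocol's independent committee, and Protocol 13.9.2, which puts the interim analyses in the sponsor's hands anyway.
- **The sponsor adjudicates alone.** The listing of a CEC form leaves open whether a committee was used. This is an ambiguity to settle.
- **The borderline example is selected.** It is. At the planned effect the result is clear of the bound, and 16 v 12 would need six rejections. The bound comes from a table labelled an example, bounds are recalculated, and SAP 5.1 spends the remaining alpha after early termination. The small planned event count is nonetheless the plan's own.

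**Conclusion.** The point holds in this form: the SAP gives the sponsor confirmation and dating of the primary endpoint in an open-label trial, states no masking, describes no route for events not reported as progression, and plans no analysis that would expose the effect of confirmation. It shows a vulnerability; the documents do not show that bias occurred or in which direction.

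Near the bound, one to three decisions out of about 28 can change the conclusion, in either direction. If 20% of Test-arm events alone were rejected, the one-sided false-positive rate would rise from 1.8% to 7.3%. If 20% were rejected in both arms, power would fall from 82.6% to 72.4%. These figures rest on assumed rejection shares, the planning rates (or 10% in both arms under no difference), a single test, and an illustrative bound.

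**What to change.** In SAP 8.3 and 10.5, before database lock:

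1. Program the candidate list from data already collected: every TTM run meeting the duration rule, every cardioversion record (listing 16.2.31) and every investigator-reported progression.
2. Have the existing adjudicators review all candidates from packets with arm and ablation history redacted, without access to comparative interim results.
3. Add a sensitivity log-rank on all investigator-reported events before confirmation, and a table of rejected and re-dated events by arm.

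In SAP section 5, reconcile the GSMC with the protocol's independent DSMC and state who saw comparative interim results. Rewording SAP 4.1 cannot undo looks already held, so disclosure is what remains. Reconcile the sponsor's role in SAP 8.3 with listing 16.2.17.2 by stating whether a CEC was used.

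The cost is SAP wording, one programmed list, one further log-rank run, one table, and modest redaction and re-review work. A newly formed committee is not required. Masking will be incomplete for events around re-ablation, because cardioversion done solely as part of such a procedure is excluded and reviewers must be able to recognise it.

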5. CHANGES TO PLANNED ANALYSIS

5.1 Changes for the final analysis

As the study was terminated early, without having met primary effectiveness or futility criteria at the most recent interim analysis, it is not fully obvious which alpha level to use for the primary efficacy analysis. However as the number and time points of the interim analyses had not been fixed in advance, it was decided to spend all alpha remaining for the final analysis, in other words to spend what is left from the total alpha. Moreover, after further discussion, it has been decided to update the calculation of the primary endpoint to use procedure date as start date for time to event calculation rather than randomization date (see section 8.3).

It also was decided to delete some of the analyses originally planned in the protocol:

- For secondary endpoint “factors associated with AF disease progression”, only the main analyses will be performed, and some of the supporting models were deleted
- Analysis of site heterogeneity will not be performed

Moreover, a sensitivity analysis for the primary endpoint and first secondary endpoint was added, using an alternative definition for the primary endpoint based on the consensus statement of the HRS (Heart Rhythm Society, 2017).

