7. ANALYSIS POPULATIONS

The following analysis populations will be used to complete the analyses of data.

Cross-over subjects will be handled differently for each type of analysis population, as described subsequently. In general, subjects from the control group who have an ablation procedure after the primary endpoint is met will not be analyzed as cross-over.

Intent to treat (ITT) population: The ITT subject population will include all

subjects randomized, where subjects will be classified by the group to which they are randomized, regardless of the treatment received. For the ITT population, cross-over subjects will be included in the Control Group per randomization. Lost-to-follow-up and withdrawn/early termination subjects will also be included in the ITT population.

Per protocol (PP) population: The PP subject population will include randomized subjects who satisfy the following criteria, according to the treatment actually received:

- **Test Group:** subjects who
 - have undergone RF ablation,
 - are treated with the study catheter (THERMOCOOL[®] Catheter Family),
 - are in compliance (no major protocol deviations that has an impact on scientific value of the study) with the study protocol, and
 - have been treated for the study-related arrhythmia.
- **Control Group:** subjects who
 - have started an investigator-prescribed AAD and completed the dose-loading period (2 weeks),
 - have not undergone RF ablation,
 - are in compliance (no major protocol deviations that have an impact on scientific value of the study) with the study protocol, and
 - have been treated for the study-related arrhythmia.

All analyses conducted in the PP population will be as treated analyses. For descriptive tables and simple inferential models with fixed treatment effects subjects who have undergone RF ablation will be included in the Test Group regardless of the original treatment assigned (original randomization). Thus, cross-over subjects will be included in the Test Group for PP analyses. For more complicated inferential analyses, models will be applied where treatment itself is included as time-dependent covariate (see section 10.2 and 10.6.4). The approach described above applies for all tables which do not summarize data by visit (e.g. for time to event endpoints and other endpoints calculated overall per-patient). For summaries by visit and repeated measurement models, cross-over subjects will be completely excluded.

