8.2 Handling of Missing Data

There will be no imputation for the primary efficacy analysis and no sensitivity analysis with multiple imputation for the ITT population as the log rank test accounts for censored (independent of the reason) observations, which is sufficient also for subjects who could not be followed up for the planned period. Other data except treatment group assignment are not required for this testing method.

For the per protocol sensitivity analysis, the same applies to the time-to-event outcome (effectiveness endpoint) data.

For the derivation of the variable 'duration of AF', incomplete dates will be imputed with the mid point of the possible interval (15th of a month if only the day is missing, 1st of July if the month is missing as well). No further imputation is planned.

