10.1 Primary Efficacy Variable Analysis

The primary analysis will be a Kaplan-Meier (KM) analysis for all subjects in the ITT population and account for censored observations. The primary effectiveness analysis will be performed in the ITT population, where the subjects will be attributed to the treatment group as randomized, regardless of treatment cross-over or post-randomization medical care. A log-rank test will be used to compare the hazard functions between the two groups at any observed event time. If observed, the median time to persistent AF/AT as well as the 95% confidence intervals will be reported by treatment group based on Kaplan-Meier estimates. The rate of survival without persistent AF/AT and rate of persistent AF/AT at 3 years follow-up as well as the 95% confidence intervals for both groups will be presented using the product limit estimate from the Kaplan Meier curve. Kaplan-Meier curves will be plotted.

The effect size is defined as the negative log of the hazard ratio (hazard rate of the Test Group over hazard rate of the Control Group): $\delta = -\log_e(\lambda_t/\lambda_c)$.

This study is to test the following hypothesis using a one-sided test at alpha equal to 0.025:

H0: $\delta \leq 0$

H1: $\delta > 0$

Null hypothesis: the hazard rate in the Test Group is greater than or equal to the hazard rate in the Control Group at observed event times during the follow-up period

Alternative hypothesis: the hazard rate in the Test Group is less than the hazard rate in the Control Group at observed event times during the follow-up period

Subjects will be considered to have an effectiveness success if they do not progress to persistent AF/AT through the 3-year follow-up period.

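### The final-analysis clock starts at the procedure in the Test group but at randomization in Control, so Test subjects with no procedure have no start date and Test events before the procedure have a negative time in a log-rank test declared ITT.

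*SAP*

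**What the plan says.** - **Time origin.** SAP 8.3 will "use date of procedure as start date for the test group, and date of randomization as start date for the control group". SAP 5.1 lists this among the changes for the final analysis, as a decision "to use procedure date as start date for time to event calculation rather than randomization date". SAP version 1.0, which governed the interim analyses, timed both arms from randomization.
- **Events.** SAP 8.3 also says: "The primary endpoint is reached at the date of the first cardioversion after randomization", except a cardioversion done solely as part of an ablation. It adds: "All events where the sponsor confirmed in their final assessment that the primary endpoint was reached will be taken into account for analysis".
- **Censoring.** SAP 8.3 censors event-free subjects at the later of the last visit and the last TTM recording. This fixes an end date only.
- **Population.** SAP 7 defines ITT as all randomized subjects, "where subjects will be classified by the group to which they are randomized, regardless of the treatment received". SAP 10.1 runs the log-rank test on that population: "the subjects will be attributed to the treatment group as randomized, regardless of treatment cross-over or post-randomization medical care". SAP 9.1 equates enrolled subjects with ITT.
- **Missing data.** SAP 8.2: "There will be no imputation for the primary efficacy analysis".
- **Who is affected.** Protocol 9.5 foresees Test subjects who are randomized but never have the study catheter inserted. Protocol 11.2.1 (transesophageal echocardiography) foresees postponed procedures. No maximum wait is stated.
- **Sensitivity analysis.** SAP 10.5 varies the event definition (HRS 2017) but not the clock.

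**The concern.** Two kinds of Test record do not fit the stated derivation.

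1. A subject with no procedure has no start date. Protocol 9.5 labels such subjects excluded, but SAP 9.1 keeps them in ITT because they are randomized. Subjects with a catheter inserted but no RF energy delivered do have a procedure date and are not affected.
2. A confirmed event between randomization and the procedure gives a negative time. It can be computed but is not a valid survival time.

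Someone must then decide whether such records are kept, moved or dropped, in the single primary test of an open-label trial, after interim analyses on a different clock. The plan tables only 28 events at the final look, so a few records can change the decision. With no analysis on the randomization clock in SAP 10.5, the effect of the change would also go unreported.

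**Working it through.** **The plan's own figure.** With 3-year rates of 15% and 5%, -ln(HR) = -ln[ln(0.95)/ln(0.85)] = 1.153 (the SAP prints 1.1541; the difference is immaterial). Schoenfeld events at one-sided 0.025 and 85% power: 4 × (1.960 + 1.036)² / 1.153² = 27.0, or about 27.7 after group-sequential inflation. The tabled 28 is reproduced.

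**Expected Test events before the procedure.** Take the planned Control hazard h = -ln(0.85)/3 = 0.0542 per year, 161 Test subjects and an assumed mean wait of w months: 161 × (1 - exp(-h·w/12)).
- w = 1: 0.7 events.
- w = 3: 2.2 events.

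These are upper values, because they assume that every event is recorded at onset. TTM starts only at Day 104.

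**Subjects with no procedure.** Suppose k of 161 are untreated and progress at r = 15% or 25%, the plan's two drug-arm rates. If kept, the Test rate is p = [(161 - k) × 0.05 + k × r]/161 and HR = ln(1 - p)/ln(0.85). If dropped, HR = ln(0.95)/ln(0.85) = 0.32.

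| Assumed share (k) | HR if kept | Type I error if dropped, r = 25% |
|---|---|---|
| 2% (3) | 0.33-0.34 | 2.8% |
| 5% (8) | 0.35-0.38 | 3.1% |
| 10% (16) | 0.38-0.45 | 4.1% |

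At r = 15%, dropping gives 2.3-2.7%. Keeping gives 2.2-2.6% throughout. These rates are at z = 1.96, with the same share and risk in both arms and subjects dropped from Test only.

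**Effect of the clock, by log-rank simulation.**
- From the plan: 161 per arm, 15% v 5% at 3 years, 10% drop-out, constant hazard.
- Assumed: waits uniform on 0 to 2w. All, half or none of the events are recorded at onset, and the rest are found at Day 104 of the arm's own Day 0 and then monthly. Test subjects carry the Control hazard until ablation.
- 6,000 replicates per cell; Monte Carlo error is about 0.2 points at 2.5% and 0.6 points at 70%.
- Single look, shown at z = 1.96 / the tabled final bound 2.0507.

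| | Mean wait 1 month | Mean wait 3 months |
|---|---|---|
| Type I, procedure clock, events kept at time 0 | 2.1-2.2% / 1.7-2.0% | 1.2-1.3% / 0.9-1.0% |
| Power, randomization clock | 82% / 79% | 74% / 71% |
| Power, procedure clock, events kept at time 0 | 80% / 77-78% | 68-69% / 64-65% |
| Power lost by the procedure clock | 1.6-2.0 points | 5.6-6.8 points |
| Kept v dropped, different decision (2.0507) | 0-5.0% | 0-16.3% |

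Over both waits, type I error is 2.4-2.8% / 2.0-2.3% on the randomization clock and 1.2-2.6% / 1.0-2.3% on the procedure clock with records dropped.

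A separate run with all events recorded at onset, at 2.0507, gave power of 79%, 77% and 82% (randomization clock, kept, dropped) at 1 month, and 70%, 65% and 82% at 3 months. The upper end of the kept-v-dropped range belongs to that case; the zero belongs to the case where no event is recorded at onset. In every power replicate where the two clocks disagreed, with events kept, the randomization clock was significant and the procedure clock was not.

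**The case against.** The change is disclosed and reasoned. Protocol Table 1 sets Day 0 at the index ablation in Test and at randomization in Control, and Protocol 11.2.1 counts Test visits from the index procedure. SAP 8.3 calls the new clock more conservative, and with pre-procedure events kept at time 0 that is right. The SAP's instruction to take every confirmed event into account points to keeping them. All of this stands. It is why the point is not more severe, but it supplies no time for either group.

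Three stronger readings are tempting, and the documents support none of them.

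- **That the change favours ablation or inflates type I error.** Dropping records can do so if the hazard is front-loaded or the dropped subjects are at higher risk. Protocol 5.1 does cite higher first-year progression (8-15%, against 3-6% a year generally). A simulated first-year hazard three times the later one, with 30 to 90 days' mean wait, 2-10% untreated and such records dropped, gave 3.2-4.6%. That stacks assumptions which the plan does not make on a dropping rule that its text opposes.
- **That the timing shows a choice driven by results.** The SAP gives a design reason, and with events kept the change works against the Test group.
- **That SAP 8.2 contradicts itself** in saying "Other data except treatment group assignment are not required for this testing method". This is better read as data beyond the time-to-event outcome. Either clock needs a start date to derive that outcome.

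**Conclusion.** The point holds as a gap in the specification of the primary analysis: the stated derivation and the declared ITT test cannot both be followed for every Test subject and confirmed event. It should be fixed. It is not evidence of bias in a known direction.

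Kept at time 0, the test is conservative and costs about 2 points of power at a 1-month mean wait and 5 to 7 at 3 months. Dropped, ITT is broken, and the decision can differ from the kept version in up to about 5% or 16% of trials at the design effect. Under the plan's constant hazard there is no material type I inflation from dropping pre-procedure events. Dropping untreated subjects matters only if they are both numerous and at higher risk.

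The waits, untreated shares and proportion of events recorded at onset are assumptions. The rates are for a single look at the planned size. SAP 5.1 says that the trial stopped early, and neither document gives the actual final event count or boundary.

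**What to change.** **Preferred.** In SAP 5.1 and 8.3, use randomization as time zero in both arms for the primary ITT log-rank test, which is the SAP version 1.0 definition. Keep no-procedure Test subjects, pre-procedure events and all other confirmed events under the existing SAP 8.3 censoring rule. Move the procedure-date clock to SAP 10.5 as a labelled sensitivity analysis, with pre-procedure events at time 0 and no-procedure subjects timed from randomization.

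**Minimum, if the procedure clock stays primary.** Write that same rule for it in SAP 8.3, add the randomization-clock analysis to SAP 10.5, and report waiting times and the counts of both groups.

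**Cost.** SAP wording and one derivation. The interim analyses already used this clock, and the data are in planned output (disposition counts, listings 16.2.5 and 16.2.15). The downside is that Test visits and TTM fall slightly later on a common clock; with TTM-only detection the simulated type I error is 2.6-2.8% at z = 1.96.

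A common 3-year cut-off from randomization should be a sensitivity analysis only. Table 1 lets the Year 3 visit run to Day 1170, 74 days past 3 years, so a cut-off could remove up to about 161 × 0.85 × 0.9 × (1 - exp(-0.0542 × 74/365.25)) = 1.3 Control events and, by the same calculation at the 5% rate, 0.7-1.1 Test events. That is about as many as the gap itself affects.
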